5.1.2. Phase Definitions

The phases in the study will be constructed as follows:

Table 6 Phase Definitions for Double-Blind Safety Analysis

Phase	Phase #	Period	Period #	Interval	
				From	To
Screening	1			Date and time of signing the informed consent form	One minute prior to start of post dose 1 period
Post-dose	2	Post-dose	1	Date and time of first vaccination	Minimum of: a) 23:59 at the date of last contact (for early discontinuation)

Statistical Analysis Plan VAC31518COV3001

				
 b) 23:59 at the date of data base cut-off date in case of interim c) 23:59 on 28 days after the first vaccination (23:59 of day of vaccination + 28 days) d) One minute before date and time of treatment unblinding e) One minute before date and time of another vaccination outside the study
Follow-up (D30-M6)	3		One minute after Post-dose 1 Period end	
Minimum of:
 
 a) 23:59 at the date of last contact (for early discontinuation) b) 23:59 at the date of data base cut-off date in case of interim c) 23:59 at date of the Month 6 (date of vaccination + 6 Months) d) One minute before date and time of treatment unblinding e) One minute before date and time of another vaccination outside the study
Follow-up (M6-W52)	4		One minute after Follow-up (D30-M6)	
Minimum of:
 
 a) 23:59 at the date of last contact (for early discontinuation) b) 23:59 at the date of data base cut-off date in case of interim c) One minute prior to Week 52 Visit d) One minute before date and time of treatment unblinding e) One minute before date and time of another vaccination outside the study
Long term Follow-up (W52-End)	5		One minute after Follow-up (M6-W52)	
Minimum of:
 
 a) 23:59 at the date of data base cut-off date in case of interim b) maximum of: 
 1. 23:59 at the date of last contact (for early discontinuation) 2. 23:59 at the date of last visit

Statistical Analysis Plan VAC31518COV3001

					
 3. One minute before date and time of treatment unblinding 4. One minute before date and time of another vaccination outside the study

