Open label Follow -up 1	6			Date and time of unblinding	
Minimum of
 
 a) 23:59 at the date of data base cut-off date in case of interim b) One minute prior to date and time of second/other vaccination within or outside the study c) Maximum of: 
 1. 23:59 at the date of last contact (for early discontinuation) 2. 23:59 at the date of last visit
Follow-up other vaccine	7			Date and time of vaccination outside the study	
Minimum of
 
 a) 23:59 at the date of data base cut-off date in case of interim b) Maximum of: 
 1. 23:59 at the date of last contact (for early discontinuation) 2. 23:59 at the date of last visit

Table 7 Phase Definition for Pooled Open Label Safety Analysis

Phase	Phase #	Period	Period #	Interval	
				From	To
Post Dose	1	Post dose	1	Date and time of Ad26.COV.2 vaccination	
Minimum of
 
 a) 23:59 at the date of data base cut-off date in case of interim b) One minute before date and time of another vaccination outside the study c) 23:59 on 28 days after the first vaccination (23:59 of day of vaccination + 28 days) d) 23:59 at the date of last contact (for early discontinuation)
Follow-up (D30-M6)	2			One minute after Post-dose 1 Period end	Minimum of:

					
 a) 23:59 at the date of last contact (for early discontinuation) b) 23:59 at the date of data base cut-off date in case of interim c) 23:59 at the date of the Month 6 (date of Ad26.COV.2 vaccination + 6 Months) d) One minute before date and time of another vaccination outside the study
Follow-up (M6-W52)	3			One minute after Follow-up (D30-M6)	
Minimum of:
 
 a) 23:59 at the date of last contact (for early discontinuation) b) 23:59 at the date of data base cut-off date in case of interim c) One minute prior to Week 52 Visit d) One minute before date and time of another vaccination outside the study
Long term Follow-up (W52-End)	4			One minute after Follow-up (M6-W52)	
Minimum of:
 
 a) 23:59 at the date of data base cut-off date in case of interim b) maximum of: 
 1. 23:59 at the date of last contact (for early discontinuation) 2. 23:59 at the date of last visit 3. One minute before date and time of another vaccination outside the study

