Safety analyses will be performed on the FAS. No formal statistical testing of safety data is planned. Safety data by double-blind vaccination group will be analyzed descriptively. Specific safety analyses will be performed on the Safety Subset. All safety analyses will be tabulated by treatment group (active vaccine, placebo) according to the as-treated principle. All safety analyses will be presented overall and by age and comorbidity (with/without) strata. The main age strata for reporting purposes are ≥ 18 to < 60 years of age and ≥ 60 years of age. In addition, safety data will be analyzed by treatment group and participant seropositivity status at screening.

For the double-blind phase, the safety data up to the unblinding date will be presented separately for the Ad26.Cov 2 double-blind group and the placebo double-blind group (Analysis I). Safety data after the unblinding date but before the open label vaccination date are listed separately.

Additionally, safety data will be pooled for all subjects that received Ad26.Cov 2 (in the double blind phase or in the open label phase) from the start of their Ad26.Cov 2 vaccination to the end of the trial (Analysis II): unsolicited AEs up to day 28, SAEs and MAAEs leading to discontinuation during the entire study, MAAEs until 6 months after last vaccination, AEs of special interest and AEs of interest during the entire study. All tables will be presented by phase.

The safety data from subjects that were unblinded and who received a vaccine outside the study will be tabulated separately.

Subjects that took another COVID-19 vaccine before being unblinded are excluded from the safety tables from the moment they received the other vaccine. The safety data from those subjects after they received the other vaccine are listed separately.

Denominator for the percentages is the number of participants in the considered population and phase for a certain regimen (incidence per 100 participants/phase).

Continuous variables will be summarized using the following statistics, as appropriate: number of observations, arithmetic mean (mean), 95% CI for the mean, standard deviation (SD), median, quartiles (Q1 and Q3), minimum and maximum. Frequencies and percentages (one decimal place) will be generated for categorical variables. No formal comparisons between groups will be provided.

Other exploratory or sensitivity analyses may be performed in addition to the analyses described below on an ad-hoc basis.

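### Table 6 phase 5 and Table 7 phase 4 put their stopping dates under a maximum, so unblinding (Table 6) and an outside vaccine (both tables) do not end the phase, contrary to section 5.7

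*SAP*

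**What the plan says.** Tables 6 and 7 in SAP section 5.1.2 give each safety phase a start and an end.

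- **Table 6, phases 2 to 4.** The end is a minimum that includes unblinding, for example "d) One minute before date and time of treatment unblinding", and outside vaccination.
- **Table 6, phase 5 (Long term Follow-up, W52-End).** The outer minimum holds only the cut-off and a nested maximum. The maximum contains last contact, last visit and then "3. One minute before date and time of treatment unblinding 4. One minute before date and time of another vaccination outside the study". The phase starts "One minute after Follow-up (M6-W52)".
- **Table 6, phase 6 (open-label follow-up).** The outer minimum contains "b) One minute prior to date and time of second/other vaccination within or outside the study". The maximum holds only last contact and last visit.
- **Table 7, phases 1 to 3.** Outside vaccination is in the minimum.
- **Table 7, phase 4.** Outside vaccination is in the maximum: "2. 23:59 at the date of last visit 3. One minute before date and time of another vaccination outside the study".

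Section 5.1.1 has safety results presented by phase. Section 5.7.1.3 allocates an adverse event to any period that contains its start. Section 5.7 states what the tables should deliver: "For the double-blind phase, the safety data up to the unblinding date will be presented separately" by double-blind group. For an outside vaccine taken before unblinding it adds: "Subjects that took another COVID-19 vaccine before being unblinded are excluded from the safety tables from the moment they received the other vaccine". Data after an outside vaccine in unblinded participants are to be tabulated separately. Sections 5.1 and 5.1.5 also limit the double-blind analysis, safety included, to onset up to unblinding.

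**The concern.** A stopping date works only inside a minimum. Inside a maximum it is overridden by any later last contact or last visit, and the SAP asks unblinded participants to stay in follow-up. The rows that close the double-blind phases (Table 6) and the pooled Ad26.COV2.S phases (Table 7) therefore do not apply the limits that section 5.7 sets.

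At stake is the attribution of serious events. Events after unblinding could be counted in a double-blind phase, including placebo recipients' events after they received Ad26.COV2.S in the study. Events after another manufacturer's vaccine could be counted as long-term Ad26.COV2.S follow-up. Denominators are exposed too, because section 5.7 uses participants per phase.

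**Working it through.** The plan gives no figure to reproduce. The check applies the written rules to example participants.

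**Rules as written**

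- Table 6 phase 5 end = min(cut-off, max(last contact, last visit, unblinding − 1 min, outside vaccination − 1 min)).
- Table 7 phase 4 end = min(cut-off, max(last contact, last visit, outside vaccination − 1 min)).
- Each of these phases starts one minute after the previous phase ends.
- Comparator, Table 6 phase 6 end = min(cut-off, second or other vaccination − 1 min, max(last contact, last visit)).

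**Inputs.** The cut-off is 9 July 2021 (section 1). The other dates are assumptions: vaccination 1 November 2020, last contact and last visit 1 July 2021, unblinding and outside vaccination at 09:00.

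**Participant A, unblinded 15 March 2021, step by step**

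1. Phase 3 ends at min(1 July, 9 July, Month 6 = 1 May, 15 March 08:59) = 15 March 08:59.
2. Phase 4 starts 15 March 09:00 and ends 15 March 08:59, so it is empty.
3. Phase 5 starts 15 March 09:00 and ends at min(9 July 23:59, max(1 July 23:59, 15 March 08:59)) = 1 July 23:59. That is 108.6 days, all after unblinding.
4. Phase 6 also starts 15 March 09:00. An event on 1 June lies in both phases.

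**Phases that receive the event**

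| Participant | Event | Table 6 as written | Table 6 corrected | Table 7 as written | Table 7 corrected |
|---|---|---|---|---|---|
| A: unblinded 15 Mar | 1 Jun | 5 and 6 | 6 | 3 | 3 |
| B: as A, outside vaccine 1 Apr | 1 Jun | 5 and 7 | 7 | 4 | none |
| C: outside vaccine 1 Apr, unblinded 1 Jun | 15 Apr | 5 and 7 | 7 | 4 | none |
| D: neither | 1 Jun | 4 | 4 | 3 | 3 |

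Table 7 entries apply if the participant received Ad26.COV2.S on 1 November. For B and C, Table 7 phase 4 then runs from 1 April 09:00 to 1 July 23:59, or 91.6 days, all after the other vaccine. Corrected means that the stopping dates sit in the outer minimum.

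**In-study crossover.** For a placebo recipient who is unblinded and then receives Ad26.COV2.S in the study, phase 6 closes one minute before that dose. Phase 7 opens only for a vaccination outside the study. Later events therefore fall in phase 5 and in no other Table 6 phase. Once corrected, phase 5 is empty for this participant, and the events appear only in Table 7, whose clock starts at that dose.

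**Does it bite at this cut-off?** From 21 September 2020 (section 5.4.8) to 9 July 2021 is 291 days, or 41.6 weeks. Week 52 is day 364, so no participant has reached it. The results for A to C and for crossover need the literal start rule, under which phase 5 opens wherever phase 4 stops. If Table 6 phase 5 and Table 7 phase 4 start only at Week 52, as labelled, both are empty at this cut-off.

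**Later analysis.** Take the same vaccination date, unblinding on 1 December 2021 (after Week 52), last contact on 1 October 2022 and no interim cut-off. Phase 5 opens on 31 October 2021 under either reading and runs to 1 October 2022. An event on 1 March 2022 falls in phases 5 and 6 as written, and in phase 6 only once corrected. With an outside vaccine on 1 December 2021 instead, Table 7 phase 4 also runs to 1 October 2022 and takes the event.

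**The case against.** The strongest reply is that the intent is clear. Sections 5.1, 5.1.5 and 5.7 all limit double-blind safety data to the time before unblinding, and section 5.7 says how data after an outside vaccine are handled. A programmer who follows that text would not produce the misallocation. This stands as evidence of intent. It does not settle the matter, because the phase tables are the operational rule and section 5.7.1.3 allocates events by their limits. That section mentions multiple allocation only for partial dates and does not resolve an overlap between phase 5 and phase 6 or 7.

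A second reply is that phase 5 is labelled W52-End, and that the effect at this cut-off uses the end time of an empty phase 4 to open phase 5. This also stands: the effect at 9 July 2021 is conditional on the literal reading.

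A third reply concerns scope, and it is correct. Efficacy censoring follows separate rules. MAAE tables use only the post-dose, D30-M6 and M6-W52 phases of Table 6 (section 5.7.1.1). Solicited events and 28-day unsolicited events are untouched, and no formal safety testing is planned.

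A layout fault from the PDF is unlikely. The numbering in the maximum runs 1 to 4 across a page break in Table 6, and 1 to 3 without a break in Table 7.

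**Conclusion.** The two cells are wrong as written. They contradict the other rows of their own tables and sections 5.1, 5.1.5 and 5.7. Read literally, they place SAEs, AESIs and deaths after unblinding or an outside vaccine in double-blind phase 5 as well as in phase 6 or 7. They leave post-crossover events of placebo recipients in phase 5 alone within Table 6. In Table 7, events after another vaccine count as Ad26.COV2.S follow-up, with no competing phase. Unblinding is not a stopping date in Table 7, so only outside vaccination is at issue there.

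Two stronger readings are tempting, and the SAP does not support them.

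- **That events after unblinding are taken out of their proper phase.** In Table 6 they are mostly allocated twice, because phases 6 and 7 still receive them. Post-crossover events are the exception within Table 6.
- **That the analysis at the 9 July 2021 cut-off certainly carries a long stretch of misallocated time.** Subtracting the approximate median double-blind follow-up of 112 days (section 5.4.3) and an assumed vaccination date 60 to 80 days after study start from 291 days gives 99 to 119 days. That date is not in the SAP, and differences of medians do not give time per participant. Follow-up to cut-off is also assumed. The figure applies only under the literal start rule; under the label reading it is 0 days.

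The size in events cannot be derived from the SAP. The consequence is confined to descriptive safety tabulations and per-phase denominators. No hypothesis test, alpha level or VE estimate changes.

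**What to change.** In Table 6 phase 5, move treatment unblinding and outside vaccination from the nested maximum to the outer minimum. In Table 7 phase 4, do the same for outside vaccination. Keep only last contact and last visit in the maximum, as Table 6 phase 6 already does.

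No separate rule on when a phase may open is needed. With the dates in the minimum, phase 5 ends one minute before it would start for anyone already stopped by unblinding or an outside vaccine, so it is empty. In-study crossover is covered because it follows unblinding.

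The cost is two table cells and the matching derivation code, with no new data. If safety outputs have already been produced from these phases, check whether phase 5 (Table 6) or phase 4 (Table 7) is populated at the 9 July 2021 cut-off. Any record there shows that the literal start rule was programmed, since no participant had reached Week 52.

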5.1.1. Study Phases

A baseline (or reference) value will be defined as the value of the last available assessment prior to the vaccination on Day 1.

The safety analysis will present all results by study phase (see Section 5.1.2). Immunogenicity results will be presented per scheduled time point as appropriate. Listings will be shown per phase and time point.

Study day or relative day is defined as follows:

- Study Day = visit date – date of Day 1 + 1; if visit date \geq date of Day 1 (date of first vaccination).
- Study Day = visit date – date of Day 1; if visit date $<$ date of Day 1 (date of first vaccination).

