Under protocol amendment 3 and 4, subjects in the placebo arm may receive the active vaccine (or another authorized vaccine). For the purpose of the safety analysis, the post dose period of the double blind phases refer to the first vaccination either with placebo or active vaccine. The post dose of the open label pooled phases refer to the active vaccination, which will be the first vaccination for the active group and the second vaccination for the placebo group after unblinding. The Open-label Pooled phases, are defined only for subjects that received a Ad26.COV.2 vaccination and start from the date that they received their Ad26.COV.2 vaccination.

When the time of the first vaccination is missing and it occurred on the same day as the randomization, the time of vaccination will be imputed with the time of randomization Otherwise,

if the date is available of the first vaccination then the time will be imputed with 00:00 before applying the phase and period derivation rules.

In case the time of the second vaccination or the vaccination outside the study is missing then time will be imputed with 00:00 if the date is available. In case of a partial date and the second vaccination or the vaccination outside the study occurred after the unblinding date, then the available info will be compared to the unblinding datetime. If the month is available and it is the same as the unblinding month then the day is imputed with the day of the unblinding. If the month is after the month of unblinding then the day is imputed with the first of that month. If the month and day are missing then the year will be compared with the year of unblinding. If the year is the same then the month and day are imputed with the day and month of the unblinding date. If the second vaccination or the vaccination outside the study occurred before being unblinded then the partial date will be compared in a similar way to the first vaccination datetime. In case the time of the unblinding datetime is missing then the time is imputed with 23:59.

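### Table 7 ends the pooled post-dose phase 28 days after the first vaccination, which for placebo crossovers is the placebo injection and contradicts the Ad26 anchor used elsewhere

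*SAP*

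**What the plan says.** SAP section 5.1.2 has two phase schemes for safety. Table 6 covers the double-blind analysis. Table 7 covers the pooled analysis of everyone who received Ad26, in either phase of the trial.

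In Table 7 the Post Dose phase begins at "Date and time of Ad26.COV.2 vaccination". It ends at the earliest of four limits, of which (c) is "23:59 on 28 days after the first vaccination (23:59 of day of vaccination + 28 days"). Table 6 uses the same words for its own Post-dose period. The next Table 7 row, Follow-up (D30-M6), begins "One minute after Post-dose 1 Period end", and one of its end limits is "23:59 at the date of the Month 6 (date of Ad26.COV.2 vaccination + 6 Months").

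The text after Table 7 explains the terms. For the double-blind scheme, "the post dose period of the double blind phases refer to the first vaccination either with placebo or active vaccine". For the pooled scheme, the post-dose period refers to the active vaccination, described as "the first vaccination for the active group and the second vaccination for the placebo group after unblinding". The same paragraph says that the pooled phases start on the date of Ad26 receipt. Section 5.7 likewise runs the pooled safety analysis (Analysis II) from the Ad26 vaccination onward.

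**The concern.** The SAP does not use the term first vaccination loosely. Section 5.1.1 ties it to study Day 1 ("date of Day 1 (date of first vaccination"), and section 5.1.2 treats first and second vaccinations as separate events with separate rules for missing times. Read with those definitions, limit (c) points a crossed-over placebo recipient back to the placebo injection. The phrase is right in Table 6 and appears to have been carried over unchanged. The Month 6 limit one row down does have the pooled anchor, "date of Ad26.COV.2 vaccination + 6 Months".

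Phase boundaries drive the output. Section 5.7.1.3 allocates an adverse event to a period by comparing its start date and time with the period's start and stop. Section 5.7 presents all Analysis II tables by phase and takes the participants in that phase as denominator. Table 6 offers no fallback: its open-label follow-up phase stops one minute before a second vaccination, and its last phase covers only vaccination outside the study. Table 7 is therefore the only scheme that covers a crossover's time after Ad26.

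**Working it through.** The SAP states no figure to reproduce here. The check is date arithmetic on the Table 7 rules.

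**Inputs**
- P = date of the placebo injection, which is the first vaccination for a crossover (sections 5.1.1 and 5.1.2).
- g = days from placebo to Ad26. The SAP does not give this interval, so a range of 14 to 180 days is assumed.
- Phase start = Ad26 date = P + g (Table 7, start column).
- Literal end under limit (c) = 23:59 on P + 28.
- End when anchored to Ad26 = 23:59 on P + g + 28.
- Literal D30-M6 start = one minute later, 00:00 on P + 29.

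**Formulas**, assuming that no other limit applies first
- Literal post-dose length, counting both end days = (P + 28) − (P + g) + 1 = 29 − g calendar days. Zero or less means no phase.
- Length when anchored to Ad26 = (P + g + 28) − (P + g) + 1 = 29 calendar days for every g.
- Days by which the literal end date precedes the start date = g − 28, if g > 28.
- Whole days before the Ad26 date that fall in D30-M6 = g − 29, if g > 29.

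| g (assumed) | Literal post-dose days | Literal end precedes start by | Whole pre-Ad26 days in D30-M6 | Post-dose days, Ad26 anchor |
|---|---|---|---|---|
| 14 | 29 − 14 = 15 | – | 0 | 29 |
| 28 | 29 − 28 = 1 | – | 0 | 29 |
| 29 | 29 − 29 = 0 | 1 day | 0 | 29 |
| 60 | none | 60 − 28 = 32 days | 60 − 29 = 31 | 29 |
| 120 | none | 120 − 28 = 92 days | 120 − 29 = 91 | 29 |
| 180 | none | 180 − 28 = 152 days | 180 − 29 = 151 | 29 |

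So the literal rule shortens the window for a crossover up to 28 days after placebo and removes it from day 29 on. With the Ad26 anchor, the window is 29 calendar days for everyone and no time before Ad26 enters a pooled phase. For the active group the first vaccination is Ad26, so both readings coincide.

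**Anchors side by side**
- Table 7, Post Dose start: Ad26.
- Table 7, Post Dose limit (c): first vaccination.
- Table 7, D30-M6, Month 6 limit: Ad26.
- Section 5.1.2, text after Table 7: Ad26, for both the post-dose period and the start of the pooled phases.
- Section 5.7, Analysis II: Ad26.

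Limit (c) is the only one of these that does not point to Ad26.

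**The case against.** The best defence is that the SAP settles the anchor itself. The paragraph after Table 7 says that the pooled post-dose period refers to the active vaccination, and for the placebo group identifies this as the second one. It also starts every pooled phase at Ad26 receipt. The parenthesis in limit (c) mentions only the day of vaccination, which fits that reading. A programmer who applied the limit literally would get impossible intervals and would probably notice. Safety data are descriptive, with no formal testing.

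Most of this stands. A reader might infer that the plan counts blinded placebo time as Ad26 follow-up, or that the pooled safety estimates are wrong. The documents do not support either: section 5.1.2 and section 5.7 both exclude time before Ad26, and the harm arises only if the table is coded without regard to them. Nor does the window always close before it opens, since a crossover within 28 days only loses part of it.

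A reader might also want a number of affected participants or person-years. The SAP gives neither the number of crossovers nor their placebo-to-Ad26 intervals. The approximate Day 112 in section 5.4.3 is a median follow-up for the final double-blind analysis, not that interval.

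What the defence does not remove is the contradiction. The explanatory paragraph states the reference vaccination but does not restate the 28-day end rule. The table is the operational specification, and its rule remains wrong for crossovers.

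**Conclusion.** Limit (c) of the Table 7 Post Dose phase is wrong as written for placebo crossovers and should be corrected. It contradicts its own row, the next row, the text after the table and section 5.7. The intended anchor, the Ad26 vaccination, is not in doubt.

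The consequence is conditional. Coded literally, the rule would leave crossovers more than 28 days after placebo without a valid post-dose phase, truncate it for earlier ones, and let D30-M6 open before the Ad26 dose (31 to 151 whole days before it, for assumed intervals of 60 to 180 days). That would distort the by-phase counts and denominators of Analysis II for crossovers. Coded as section 5.1.2 explains, the misallocated time is zero. The day counts rest on the assumed intervals, and no overall size can be stated from the document.

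**What to change.** In Table 7, phase 1 (Post Dose), limit (c), replace *the first vaccination* with *the Ad26.COV2.S vaccination*, to match the start column and the Month 6 limit. Then confirm that the phase derivation program uses this anchor, for example by checking that no crossover has a post-dose end before its start and that no pooled phase begins before the Ad26 date and time. The start rule itself is already in section 5.1.2 and needs no addition. The cost is one line of SAP text and a check of the program; no new data are needed.
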